7. DATA COLLECTION AND MANAGEMENT

7.1 Data Quality Assurance

During study conduct, the MedStar Georgetown University Hospital/Lombardi Comprehensive Cancer Center Quality Assurance Office (QAO) and/or Project Manager(s) (PM) will conduct periodic monitoring to ensure that the protocol and Good Clinical Practices (GCPs) are being followed. The LCCC/QAO or PM monitors may review source documents to confirm that the data recorded on CRFs is accurate. The investigator and institution will allow Pfizer monitors/auditors or its agents and appropriate regulatory authorities direct access to source documents to perform this verification.

The study site may be subject to review by the IRB, and/or to quality assurance audits performed by Pfizer, or companies working with or on behalf of Pfizer, and/or to inspection by appropriate regulatory authorities. It is important that the investigator(s) and their relevant personnel are available during the monitoring visits and possible audits or inspections and that sufficient time is devoted to the process.

7.2 Electronic Case Report Forms

As used in this protocol, the term CRF should be understood to refer to an electronic data record. A CRF is required and should be completed for each included patient.

The investigator has ultimate responsibility for the collection and reporting of all clinical, safety and laboratory data entered on the CRFs and any other data collection forms (source documents) and ensuring that they are accurate, authentic / original, attributable, complete, consistent, legible, timely (contemporaneous), enduring and available when required. Laboratory results and concomitant medications will be collected on the CRFs. The CRFs must be signed by the investigator or by an authorized staff member to attest that the data contained on the CRFs is true. Any corrections to entries made in the CRFs or source documents must be dated, initialed and explained (if necessary) and should not obscure the original entry.

7.3 Source Data Documentation

In most cases, the source documents are the hospital's or the physician's patient chart. In these cases, data collected on the CRFs must match the data in those charts. In some cases, the CRF, or part of the CRF, may also serve as source documents. In these cases, a document should be available at the investigator's site as well as at Pfizer and clearly identify those data that will be recorded in the CRF, and for which the CRF will stand as the source document.

7.4 Retention of Records

To enable evaluations and/or audits from regulatory authorities or Pfizer, the investigator agrees to keep records, including the identity of all participating patients (sufficient information to link records, e.g., CRFs and hospital records), all original signed informed consent documents, copies of all CRFs, safety reporting forms, source documents, and detailed records of treatment disposition, and adequate documentation of relevant correspondence (e.g., letters, meeting minutes, telephone calls reports). The records should be retained by the investigator according to International Conference on Harmonization (ICH), local regulations, or as specified in the Clinical Study Agreement (CSA), whichever is longer.

If the investigator becomes unable for any reason to continue to retain study records for the required period (e.g., retirement, relocation), Pfizer should be prospectively notified. The study records must be transferred to a designee acceptable to Pfizer, such as another investigator, another institution, or to an independent third party arranged by Pfizer. Investigator records must be kept for a minimum of 15 years after completion or discontinuation of the study or for longer if required by applicable local regulations.

The investigator must obtain Pfizer's written permission before disposing of any records, even if retention requirements have been met.

8. ETHICAL CONSIDERATIONS

8.1 Institutional Review Board or Ethics Committee

All oncology clinical research protocols must be submitted to the Clinical Research Committee (CRC) for scientific review before submission to and final approval by the IRB. The initial review includes an assessment of the specific plans for data and safety monitoring, which vary depending on the study type, phase, size, and sponsorship.

It is expected that the IRB will have the proper representation and function in accordance with federally mandated regulations. The IRB should approve the consent form and protocol. In obtaining and documenting informed consent, the investigator should comply with the applicable regulatory requirement(s), and should adhere to Good Clinical Practice (GCP) and to ethical principles that have their origin in the Declaration of Helsinki.

It is the responsibility of the investigator to have prospective approval of the study protocol, protocol amendments, informed consent documents, and other relevant documents, e.g., recruitment advertisements, if applicable, from the IRB. All correspondence with the IRB/EC should be retained in the Investigator File. Copies of IRB approvals should be forwarded to Pfizer.

In addition, the study will be conducted in accordance with the protocol, the ICH guideline on GCP, and applicable local regulatory requirements and laws.

8.2 Informed Consent

This study will be conducted in accordance with FDA regulations, the International Conference on Harmonization (ICH) E6 Guideline for Good Clinical Practice (GCP), the Declaration of Helsinki, and applicable local, state, and federal laws. The informed consent/assent document(s) used during the informed consent process must be reviewed by the Sponsor, approved by the IRB before use, and available for inspection. The investigator must ensure that each study patient, or his/her legally acceptable representative, is fully informed about the nature and objectives of the study and possible risks associated with participation. Whenever consent is obtained from a patient's legally acceptable representative, the patient's assent (affirmative agreement) must subsequently be obtained when the subject has the capacity to provide assent, as determined by the IRB/EC. If the investigator determines that a patient's decisional capacity is so limited she cannot reasonably be consulted, as permitted by the IRB and consistent with local regulatory and legal requirements, then the patient's assent may be waived with source documentation of the reason assent was not obtained. If the study patient does not provide her own consent, the source documents must record why the patient did not provide consent (e.g., decisionally impaired adult), how the investigator determined that the person signing the consent was the subject's legally acceptable representative, the consent signer's relationship to the study

subject and that the patient's assent was obtained, or waived. If assent is obtained verbally it must be documented in the source documents.

The investigator, or a person designated by the investigator, will obtain written informed consent from each patient or the patient's legally acceptable representative before any study- specific activity is performed, unless a waiver of informed consent has been granted by an IRB. The investigator will retain the original of each patient's signed consent/assent document.

Patients will be informed that participation is voluntary and not necessary for receiving standard of care chemotherapy for their cancer and that they can choose to withdraw consent from the study at any time. This will also be documented in writing on the consent form.

The study will not include participants less than 18 years of age. For adult participants who lack decision-making capacity, the legally authorized representative will serve as the proxy. In the event a patient or their proxy does not read, write, or understand English, a trained medical interpreter must be present, either in person or via phone or video remote access, to translate.

8.3 Subject Compensation

Subjects will not be compensated in cash or in kind.

8.4 Confidentiality

All parties will ensure protection of patient personal data and will not include patient names or other identifiable data in any reports, publications, or other disclosures, except where required by laws. Personal information about the patients, including but not limited to name, date of birth, sex, race, ethnicity, previous treatment (including but not limited to pathology reports, imaging reports, laboratory reports, surgery, radiation oncology, medical oncology, etc.), office notes, physical exam, history, medications, adverse events, etc. will be collected on each study patient. This data is important for evaluating the primary and secondary endpoints of the study and will be protected from improper use and disclosure as per MedStar standard operating procedures. This plan will be implemented at the time of signing consent for each patient.

Protected Health Information (PHI) will be accessed in this study. PHI will be received via a CRF and also be recorded in a CRF. PHI information will be retained until all follow up publications and studies stemming from this study have been completed. This information will only be shared within the research team. Confidentiality will be maintained via standard MedStar standard operating procedures. All electronic transmission of PHI data will be in encrypted/secured form. No names of subjects will be included in the publication. No digital, video, audio, or photographic recordings of the subject will be made public.

When study data is compiled for transfer to any authorized parties, patient names, addresses and other identifiable data will be replaced by a numerical code consisting of a numbering system in order to de-identify study patients. The study site will maintain a confidential list of subjects who participated in the study linking their numerical code to the subject's actual identity. In case of data transfer, Pfizer will

maintain high standards of confidentiality and protection of patient personal data consistent with applicable privacy laws.

All hardcopy and electronic data will be kept in accordance with the MedStar standard operating procedures. Upon completion of all publications related to this study, the data will be destroyed in accordance with institutional protocols. No members other than those on the research team will have access to the study data. Data will not be shared outside of the research team.

8.5 Reporting of Safety Issues and Serious Breaches of the Protocol or ICH GCP

In the event of any prohibition or restriction imposed (i.e., clinical hold) by an applicable Competent Authority, or if the investigator is aware of any new information which might influence the evaluation of the benefits and risks of the investigational product, Pfizer should be informed immediately.

In addition, the investigator will inform Pfizer immediately of any urgent safety measures taken by the investigator to protect the study patients against any immediate hazard, and of any serious breaches of this protocol or of ICH GCP that the investigator becomes aware of. Except for an emergency situation in which proper care for the protection, safety, and well-being of the study patient requires alternative treatment, the study shall be conducted exactly as described in the approved protocol.

- a. Emergency Modifications: Investigators may implement a deviation from, or a change of, the protocol to eliminate an immediate hazard(s) to trial subjects without prior IRB approval. For any such emergency modification implemented, an IRB modification form must be completed within five (5) business days of making the change.
- b. Single Patient/Subject Exceptions: Any request to enroll a single subject who does not meet all the eligibility criteria of this study requires the approval of the Principal Investigator and the IRB.
- c. Other Protocol Deviations/Violations: All other planned deviations from the protocol must have prior approval by the Principal Investigator and the IRB. According to the IRB, a protocol deviation is any unplanned variance from an IRB approved protocol that:
 - Is generally noted or recognized after it occurs
 - Has no substantive effect on the risks to research participants
 - Has no substantive effect on the scientific integrity of the research plan or the value of the data collected
 - Did not result from willful or knowing misconduct on the part of the investigator(s).

An unplanned protocol variance is considered a violation if the variance:

- Has harmed or increased the risk of harm to one or more research participants.
- Has damaged the scientific integrity of the data collected for the study.
- Results from willful or knowing misconduct on the part of the investigator(s).

- Demonstrates serious or continuing noncompliance with federal regulations, State laws, or University policies.

If a deviation or violation occurs without prior approval from the Principal Investigator, please follow the guidelines below:

- A) Protocol Deviations: Personnel will report to any sponsor or data and safety monitoring committee in accordance with their policies. Minor deviations should be summarized and reported to the IRB at the time of continuing review. Major deviations should be summarized and reported to the Regulatory Affairs Coordinator who will submit to the IRB as soon as possible, but not more than 10 calendar days after acquiring information reasonably suggesting that a reportable (major) deviation has occurred.
- B) Protocol Violations: Violations should be reported by study personnel within one (1) week of the investigator becoming aware of the event using the same IRB online mechanism used to report Unanticipated Problems.

8.6 Amendments to the Protocol

Should amendments to the protocol be required, the amendments will be originated and documented by the Principal Investigator. It should also be noted that when an amendment to the protocol substantially alters the study design or the potential risk to the patient, a revised consent form might be required. The written amendment, and if required the amended consent form, must be sent to the IRB for approval prior to implementation.

8.7 Financial Disclosure

Investigators will provide Pfizer and regulatory authorities with adequate and accurate financial information in accordance with local regulations and laws in order to allow Pfizer to submit complete and accurate financial certification or disclosure statements to the appropriate health authorities. Investigators are responsible for providing updated information on financial interests during the course of the study as well as for 1 year after completion of the study.

Any investigator who has a conflict of interest with this study (patent ownership, royalties, or financial gain greater than the minimum allowable by their institution, etc.) must have the conflict reviewed by MHRI or LCCC. All investigators will follow the MHRI and LCCC conflict of interest policy.

8.8 Adherence to the Protocol

Except for an emergency situation in which proper care for the protection, safety, and well-being of the study patient requires alternative treatment, the study shall be conducted exactly as described in the approved protocol. Minor deviations should be summarized and reported to the IRB at the time of continuing review. Major deviations should be summarized and reported to the Regulatory Affairs Coordinator who will submit to the IRB as soon as possible, but not more than 10 calendar days after acquiring information reasonably suggesting that a reportable (major) deviation has occurred.

9. REQUIRED DOCUMENTATION

Before the study can be initiated at any site, the following documents must be filed at MGUH Regulatory (Study Binder):

- Original U.S. FDA Form 1572. The names of all investigators must appear on this form. Investigators must also complete all regulatory documentation as required by local and national regulations;
- Sponsor-PI's and sub-Investigator's medical licenses, CITI training, Current curriculum vitae
- Written documentation of IRB approval of protocol and informed consent document;
- A copy of approved protocol
- A copy of the IRB-approved informed consent document and IRB communications;
- CRC communication
- A signed Clinical Research Agreement
- Delegation of authority log
- Lab CAP/CLIA, Laboratory normals
- Any sponsor communication, including newsletters
- Monitoring visits letters – pre/post

Appendix A: Study procedures

	Screening Phase		Treatment Phase		Pre-surgery	Surgery	Follow up Phase	
Procedure	Screening	Pre-treatment	Treatment start	Last day of treatment	Pre-surgery	Day of Surgery	End of Treatment visit	Long term follow up
Day	(-28 to -1)	(-28 to 0)	1	12	13 +/-1	15 +/-1	32 (+/- 8 days)	1yr and 5yr
Signed Informed Consent Form(s)	x							
Review of Eligibility Criteria	x	x						
Clinical Visit	x ⁹	x ⁷			x ⁷		x	
Review of breast US, Mammograms and breast MRI if available	x							
Disease status	x	x ⁴			x ⁴		x	x ⁶
CTCAE v. 4.03 review of baseline toxicities		x			x ⁴		x	
Archival tumor tissue specimen or 15 unstained slides	x							
Rb testing archival tissue	x ¹							
Tissue for research at definitive surgery						x ⁵		
CBC/diff/platelets	x ⁸	x ⁴			x ⁴		x	
CMP	x ⁸	x ⁴			x ⁴		x	
Coags (aPTT, INR)	x ⁸							
Serum or urine pregnancy test	x							
Blood sample for research - cells		x ²			x ^{2,4}		x ²	

	Screening Phase		Treatment Phase		Pre-surgery	Surgery	Follow up Phase	
Procedure	Screening	Pre-treatment	Treatment start	Last day of treatment	Pre-surgery	Day of Surgery	End of Treatment visit	Long term follow up
Day	(-28 to -1)	(-28 to 0)	1	12	13 +/-1	15 +/-1	32 (+/- 8 days)	1yr and 5yr
Schedule definitive surgery date		x						
Group A: Start palbociclib			x ³					
Group B: no treatment								
Lumpectomy or mastectomy						x		
Pathologic exam of specimen						x		
EMR review							x	1yr and 5yr
Telephone contact							x	1yr and 5yr

1 Rb testing for all participants at screening. Rb negative configures screen failure.

2 Research blood sample for liquid biopsy and tissue banking (serum/plasma and PBMCs). In Group B, pre-operative sample can be drawn any time after consenting and prior to surgery. For details on these samples please refer to item **4.5.2.7 Mandatory Blood Samples for Biomarker Analysis**

3 Palbociclib 100mg PO daily for 12 days; provided by Pfizer and to be dispensed by MGUH/WHC research pharmacy.

4 Group A only.

5 Tissue sample #2: Under supervision of the certified pathologist, the sample required for pathologic diagnosis will be collected. Excess tissue will be used for research. Research tumor samples will be collected for H&E and IHC (formalin), CRC cultures (conditionally reprogrammed cell media), isolation of RNA and subsequent expression analysis, and for proteomic or metabolomic analysis (Snap Frozen). Non used tissue will be banked. Handling, processing, storage and testing DCIS sample at definitive surgery by pathologist and at Lombardi Research Lab ([name] LAB)

6 Evaluation of clinical characteristics including disease status by EMR review and telephone contact

[figure not shown]
7 Additional visits will be required for patients enrolled on Group A. These include a visit with Medical Oncology team prior to initiation of palbociclib (pre-Treatment) and another visit after end of palbociclib, prior to surgery (pre-Surgery). These visits are not required for patients enrolled in Group B.

8 Tests must be completed at least 5 days prior to definitive surgery in Group B (untreated)

9 Clinical visit -(28) to (-1) is the routine visit typically with the surgeon to discuss newly diagnosed DCIS and surgical plan, at which point the study may be offered to the patient (Group A and B).

[figure not shown]

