2.3 Outcome Measures

Feasibility: the approach will be considered feasible if more than 50% of the enrolled patients are treated and followed within protocol rules, if collected samples are suitable for studies, and if pathologic changes are detectable when comparing diagnostic and surgical specimens, or treated and untreated specimens. In Group A, patients will be treated with palbociclib alone, providing the opportunity to address if proposing this kind of treatment for these patients is feasible. Obtaining human data and feasibility data would be key for designing efficacy/definitive studies of palbociclib in DCIS.

Pathology: we will perform descriptive analysis of microscopic and molecular changes upon exposure to palbociclib. Biological markers will be tested by immune histochemistry (IHC). Source for comparison will be pretreatment versus post-treatment paired samples. This study will represent an opportunity to describe potential pathological changes triggered by palbociclib as a single agent in DCIS.

Toxicity: will be evaluated by CTCAE. There is no plan to compare Groups A and B regarding efficacy or toxicity. Toxicity will be descriptive for each treatment group, independently.

Correlative science: Will be performed at Lombardi Comprehensive Cancer Center. Preliminary data for this proposal was obtained using a well-established model of DCIS progression with the human MCF-DCIS cell line^{45,47}. Proposed translational components are currently routinely done at LCCC. There is no plan to compare Groups A and B regarding translational changes. Paired samples (pre- and post-systemic therapy) will be compared within the respective Group. **DCIS Sample #1** is the core biopsy

done for diagnosis, **DCIS Sample #2** is collected at definitive surgery; both collected from the same patient (paired).

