Collection of tissue at definitive surgery (sample #2): A certified pathologist will be responsible for tissue handling and destination to research. Unfortunately, performing a research-only core at surgery is not felt to be practical in patients with diagnosis of DCIS, since one of the key components of pathologic exam is to rule out invasive component. Therefore, an additional core at surgery is not felt to be safe for patients. Tissue will be collected for translational studies based on certified pathologist examination of material and without compromise of definitive diagnosis. There is a possibility that at definitive surgery invasive lesions are detected. We will describe the same parameters for DCIS lesions and for invasive lesions. Invasive component histologic abnormalities description will be purely exploratory. The focus of this study is DCIS. Pathologist will fill out a form confirming collection of sample for the trial ([Appendix L](#))

Follow up period: Patients will be followed at the postoperative period in the outpatient setting, at which point any additional systemic treatment for DCIS or invasive breast cancer will be discussed. The End of Study visit will occur approximately 2 to 3 weeks after surgery. The Informed Consent form will contain terminology asking patients for permission for the researchers to review the medical chart at 1 year and at 5 years from enrollment to collect additional clinical information about medical history, disease status and treatments.

The study procedures are summarized in [Appendix A](#).

The study schema is presented in [Appendix B](#).

The calendar template for treatment and visits timeline planning based on surgery date for patients enrolled on treatment Group A (Palbociclib) is presented in [Appendix C](#).

The Enrollment Process to Treatment Overview is presented in [Appendix D](#).

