6. STATISTICAL CONSIDERATIONS AND ANALYSIS PLAN

6.1 Determination of Sample Size

There will be two participating centers in this study: MGUH and MWHC. This is a prospective pilot study designed to assess the feasibility and potential translational changes of preoperative treatment with palbociclib of patients with Rb positive DCIS of the breast. The primary endpoints are feasibility and pathologic changes (histology, IHC and molecular analysis) comparing paired samples from before and after short course of systemic treatment (diagnostic core vs definitive surgery, in each patient). The secondary endpoint is descriptive toxicity.

The estimated sample size of 12 patients per study Group is decided based on typical sample size requirement for a pilot study⁵⁶ because parameters for expected pathologic changes caused by palbociclib in this disease are not available. *The total number of patients in this study will be 24.* The statistical analysis will be mostly descriptive due to the nature of the study and the small sample size. It will be performed after study completion. Baseline and follow-up data will be summarized using basic descriptive statistics such as means and standard deviations for the continuous variables and frequencies and percentages for categorical variables. For continuous outcome, the median and range will be reported. For binomial outcome, the proportion will be estimated along with its confidence interval estimated using exact method. Changes in the tumor histologic or molecular parameters from baseline to end of treatment will be tested using paired t-tests for continuous variables and McNemar's test for paired proportions. Repeated measures data will be analyzed using linear growth curve models that will allow us to identify and estimate individual-level growth tracks for the patients. Survival models (time to event) will be used as sample size permits to evaluate disease progression among all patients.

LCCC Biostat Unit will be responsible for designing the study and conducting data analysis which will be directed by [name].

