Appendix L: Pathology Form

Preoperative palbociclib in patients with DCIS of the breast that are candidates for surgery: WI223281

Subject Registration Number on Study: _____

Study ID (IRB#): **2018-0075**

Date _____/_____/_____

Name of Pathologist: _____ Signature: _____

Person filling the form if different than pathologist:

_____ Signature: _____

Definitive surgery: Mastectomy Lumpectomy

Check list:

- Sample collected for routine pathology exam

Research sample:

- No sample available for Research
- Sample collected for research

Research procedures:

- Sample in Research Media for [name]'s lab
- Sample in CRC media
- Sample delivered at [name]'s lab on date: _____/_____/_____

Time: _____:_____ AM/PM

By _____ (Name)

PLEASE SCAN THIS COMPLETED FORM TO THE PATIENT'S ELECTRONIC MEDICAL RECORD

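### The feasibility criterion for tissue counts only samples that were collected, and nothing says how a patient without a usable surgical sample is handled in the paired marker tests

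*Combined protocol and SAP*

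**What the plan says.** Section 3.1.1 rules out a research-only core at surgery and gives diagnosis priority: "Tissue will be collected for translational studies based on certified pathologist examination of material and without compromise of definitive diagnosis". Appendix A, footnote 5, adds: "Excess tissue will be used for research". That excess is to serve H&E and IHC, cell culture, RNA expression, and proteomic or metabolomic work. The Appendix L form includes the option "No sample available for Research" and has no field for the reason.

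Section 6.1 makes pathologic change a primary endpoint, "comparing paired samples from before and after short course of systemic treatment". On the analysis it says: "Changes in the tumor histologic or molecular parameters from baseline to end of treatment will be tested using paired t-tests for continuous variables", with McNemar's test for paired proportions. It has no rule for a missing pair or for a surgical specimen without residual DCIS. The replacement rules (sections 3.3.2 and 4.6) cover patients without surgery, Group A patients who never took palbociclib, and those who were non-compliant or stopped treatment. They do not cover patients without a surgical research sample.

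The feasibility rule in section 2.3 has three parts:

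1. "more than 50% of the enrolled patients are treated and followed within protocol rules"
2. "if collected samples are suitable for studies"
3. "if pathologic changes are detectable when comparing diagnostic and surgical specimens, or treated and untreated specimens"

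Only the first carries a threshold.

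**The concern.** Feasibility and pathologic change are both primary objectives, and section 1.3.2 says the results are meant to support the design of a larger efficacy study. Whether paired tissue can be obtained at all is one of the main things a pilot of this kind should establish. As worded, the tissue criterion looks only at the samples that were obtained. A centre that often fails to obtain tissue can still satisfy it.

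The second issue is the paired marker analysis. A surgical sample may lack usable DCIS for several reasons: the lesion was small, the diagnostic biopsy removed much of it, diagnosis used the tissue, or the lesion regressed on drug. Only the last is drug response. The plan does not record which reason applied, so the analyst could not later tell uninformative loss from informative loss.

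**Working it through.** **The plan's own figures.** The 12 per group cannot be re-derived. Section 6.1 takes it from customary pilot practice and gives no effect size, SD, alpha or power. What can be checked agrees: 2 × 12 = 24, and with Rb positivity at the stated 80% floor, 24 / 0.80 = 30, the screening number in section 3.1.1. That figure allows for Rb-negative patients only, not for missing surgical samples.

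**Feasibility, part 2.** Let k of 12 operated patients in a group have no sample, and suppose every collected sample is suitable. The documents give no rate, so k is a range. Exact (Clopper–Pearson) limits for x of n are Beta(0.025; x, n−x+1) and Beta(0.975; x+1, n−x).

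| k missing | Among collected | Among all operated | Exact 95% CI (all operated) |
|---|---|---|---|
| 2 | 10/10 = 100% | 10/12 = 83% | 52–98% |
| 4 | 8/8 = 100% | 8/12 = 67% | 35–90% |
| 6 | 6/6 = 100% | 6/12 = 50% | 21–79% |

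The first column never moves. If the more-than-50% bar of part 1 were also applied to tissue (an assumption), 6/12 would fail while 6/6 passes.

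**Feasibility, parts 1 and 3.** Part 1 counts enrolled patients, so a patient without a sample stays in. Part 3 refers to diagnostic and surgical specimens and is not limited to research tissue. Neither depends on k through its wording.

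**Paired marker test.** Assumptions, none of them in the documents: 12 normally distributed differences with SD 1, two-sided alpha 0.05, and a true change of 0.89 SD, chosen because it gives 80% power at n = 12.

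Power with random loss is 1 − F(t; n−1, 0.89√n), where F is the noncentral t distribution and t is the 97.5% point of t on n−1 df:

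- n = 12: t = 2.201, noncentrality 3.083, power 80%
- n = 10: t = 2.262, noncentrality 2.814, power 71%
- n = 9: t = 2.306, noncentrality 2.670, power 65%

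In these random-loss cases the expected estimate stays at 0.89 SD.

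In the worst case, the k best responders are exactly those without a pair (simulation):

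| Best responders lost | Mean estimate | Power |
|---|---|---|
| 1 | 0.74 SD | 69% |
| 2 | 0.62 SD | 56–57% |
| 3 | 0.50 SD | 44% |

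Between these extremes, with two pairs lost and a correlation of 0.3 to 0.7 between loss and response, the mean estimate is 0.81 to 0.70 SD and power 64% to 57–58%.

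McNemar's exact test has minimum two-sided p = 2 × 0.5^m for m discordant pairs: 0.031 at m = 6 and 0.0625 at m = 5. With five or fewer discordant pairs it cannot reach 0.05.

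**The case against.** A reader might infer that patients without residual DCIS drop out of the feasibility rule altogether, and that the plan is therefore biased against the drug. The documents do not support either step. Parts 1 and 3 of the rule retain these patients, and loss of DCIS seen in the surgical specimen could itself be a detectable change under part 3. For part 2 the error runs the other way, toward declaring success.

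A reader might also infer that these patients leave the whole pathology endpoint. They do not. Section 2.2.1 includes gross pathology and H&E, and Appendix A schedules a routine pathologic examination of the surgical specimen separately from the research tissue. The loss is confined to IHC and molecular pairs.

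Nor do the documents show that missingness depends on response. Section 1.3.2 says nothing is known about palbociclib's activity in human DCIS, and the regression data in section 1.3.1 come from a mouse model. Criterion I.7 bars complete resection at a biopsy done for eligibility, which limits one competing cause without excluding it.

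Finally, section 6.1 describes a mostly descriptive analysis and claims no power, so a fall from 80% is an illustration and not a broken promise. Part 2 also states no formal proportion.

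All of this narrows the point. It does not supply a denominator or threshold for the tissue criterion, or a rule for a missing pair.

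**Conclusion.** The point holds in a limited form. The tissue part of the feasibility rule ignores failed collections and has no threshold, so it can give too favourable an answer; 6/6 in place of 6/12 is an example, not a forecast. Patients without a usable surgical sample are absent from the paired IHC and molecular tests, and no rule covers them.

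Bias toward no effect in those tests is conditional on tissue loss tracking drug response. If loss is unrelated to response, the cost is precision alone. The SD and power figures rest on an assumed effect, alpha and loss pattern, and removal of exactly the best responders is the extreme case. This is a cheap improvement to a descriptive pilot, not a flaw that invalidates it.

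**What to change.** 1. In section 2.3, define the tissue criterion as evaluable pre/post pairs over all operated patients, per group, with an exact confidence interval and a stated threshold. Patients with no sample and patients with no residual DCIS stay in the denominator.
2. Add the reason for a missing sample to Appendix L (no residual DCIS, too little tissue, logistics). Report absent residual DCIS as its own category in each group, and do not score absence automatically as response. Group B gives descriptive background only, because patients choose their group and section 2.3 plans no translational comparison of A with B.
3. When DCIS is present but no excess tissue exists, cut IHC sections from the surgical diagnostic FFPE block after sign-out, where the pathologist permits. This recovers pairs lost for want of excess tissue; it cannot recover pairs where no DCIS remains.

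The cost is some wording, one form field and a few extra sections from existing blocks, with no new patient procedure. The downside is that the reported feasibility proportion will look less favourable.
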